## 6.2.2.2 Secondary efficacy variables and analysis

Secondary efficacy variables include:

• Incidence rate of seronegative conversion measured and confirmed by two types of assay (recombinant ELISA and IHA) in subjects who were randomized and received at least one dose of the 30-day nifurtimox treatment regimen

- Proportion of responders who show both seronegative conversion by two types of assays (recombinant ELISA and IHA) and no evidence of established cardiomyopathy as measured by ECG
- Serial reduction of OD measured by recombinant ELISA and total purified antigen ELISA

Analysis of secondary efficacy variables

The OD values from individual conventional ELISA tests (recombinant ELISA and total purified antigen ELISA) will be analyzed descriptively. Changes from baseline will be summarized to show any serial reduction of OD values. Baseline is defined as the OD values from the same ELISA tests measured at Visit 1 in part 1 of the study.

The proportion of subjects who show both seronegative conversion as confirmed by two assays (recombinant ELISA and IHA) and no evidence of established cardiomyopathy as measured by ECG will be calculated overall and by treatment regimen.

The same method for calculating incidence rate and its 2-sided 95% CI of the primary efficacy variable will be applied on the following variable:

• Incidence rate of seronegative conversion measured and confirmed by two types of assay (recombinant ELISA and IHA) in subjects who were randomized and received at least one dose of the 30-day nifurtimox treatment regimen

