- 3. Subjects with clinical manifestations of Chagas' disease, such as:
 - Known evidence of Chagas' disease-related gastrointestinal dysfunction (e.g., megaesophagus, megacolon, or both) or Chagas' digestive disease
 - Serious manifestations of acute Chagas' disease, including myocarditis, meningoencephalitis, or pneumonitis
- 4. Immuno-compromised subjects (e.g., those with human immunodeficiency virus infection, primary immunodeficiency, or prolonged treatment with corticosteroids or other immunosuppressive drugs)
- 5. Subjects who the investigator considers unlikely to adhere to the protocol, or complete the long-term follow-up
- 6. Subjects with close affiliation with the investigational site; e.g., a close relative of the investigator, dependent person (e.g., employee or student of the investigational site)

Justification of selection criteria for part 2 (CHICO SECURE)

This LTFU has been designed at the request of the US FDA to assess the incidence of seronegative conversion in subjects who were randomized and received at least one dose of nifurtimox treatment for 4 years after end of nifurtimox treatment.

For assessment of conversion of serological response to negative, 2 distinct serologic tests are recommended that use different techniques and/or detect antibodies to different antigens. Two commonly used techniques are ELISA and IHA.

The exclusion criteria are valid for known or suspected conditions and are chosen to ensure that subjects with conditions which may have an effect on the aims of the follow-up are excluded.

Considering that the follow-up period is evaluating long-term seronegative conversion and OD reduction measured by ELISA after nifurtimox treatment, subjects who required antitrypanosomal treatment, including any investigational treatment for Chagas' disease after nifurtimox regimens will be analyzed separately.

To reduce the risk of reinfection as a confounding factor in the study, subjects residing in areas where vector control has not been instituted are excluded as well.

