## 4. General Statistical Considerations

## 4.1 General Principles

The statistical evaluation will be performed using the software package SAS release 9.2 or higher (SAS Institute Inc., Cary, NC, USA). Unless otherwise specified, all significance tests will be conducted using a 2-sided alpha level of 0.05, and confidence intervals (CIs) will be 2-sided 95% intervals. All variables collected in this study will be summarized with descriptive statistics at each assessment time. For continuous variables, descriptive statistics will include the number of data available and missing data, means, standard deviations, medians, minimums, and maximums. For categorical variables, frequency counts and percentages will be provided. These will be calculated for each age stratum by treatment regimen, as well as the overall set of study subjects.

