## Part 2 (CHICO SECURE)

#### Full analysis set (FAS)

The efficacy analyses will be done using the full analysis set (FAS), as defined in part 1. Subjects will be analyzed as randomized in part 1 (CHICO) of the study.

Analyses of safety and background data will be performed on the FAS. For safety analyses, subjects will be analyzed as treated in part 1 of the study.

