## 6.2.2 Part 2 (CHICO SECURE)

## 6.2.2.1 Primary efficacy variable and analysis

## Primary efficacy variable

The primary efficacy variable will be the incidence rate of seronegative conversion measured and confirmed by two types of assay (recombinant ELISA and IHA) in subjects who were randomized and received at least one dose of the 60-day nifurtimox treatment regimen. Both test results should be negative for the subject to be considered as seroconverted. Incidence rate is the number of new cases of seronegative conversion over the study period (i.e. 4 years after end of nifurtimox treatment) divided by the person-time at risk.

Subjects used antitrypanosomal drugs during the study before they were seroconverted will not be considered as sero-convertion, but their time of observation till when they took antitrypanosomal drugs will be factored into the person time calculation.

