## 6.2.2.3 Exploratory efficacy analysis and analysis

Exploratory efficacy variables include:

- Incidence rate of seroconversion measured and confirmed by two types of assay (recombinant ELISA and IHA) in subjects by age categories (≤2 years, >2 years to ≤6 years, >6 to ≤12 years, >12 to <18 years; age is defined as subject's age at randomization)
- Proportion of presence of parasite or positive serology in babies born of mothers who were randomized and received at least one dose of either the 60- or 30-day nifurtimox treatment regimen
- Proportion of responders and incidence rate of seronegative conversion as confirmed by non-conventional serology in subjects who were randomized and received at least one dose of either 60- or 30-day nifurtimox treatment regimens

Analysis of exploratory efficacy variables

The same method for calculating incidence rate and its 2-sided 95% CI of the primary efficacy variable will be applied on the following variable:

Statistical Analysis Plan

- Incidence rate of nifurtimox subjects with seronegative conversion in all subjects by age categories. The age categories are grouped as  $\leq 2$  years,  $\geq 2$  years to  $\leq 6$  years,  $\geq 6$  to  $\leq 12$  years,  $\geq 12$  to <18; age is defined as subject's age at randomization
- Incidence rate of seronegative conversion as confirmed by non-conventional serology in subjects who were randomized and received at least one dose of either 60- or 30- day nifurtimox treatment regimens

The proportion of subjects with seronegative conversion as confirmed by non-conventional serology will be calculated overall and by treatment regimen. The numeric results of non-conventional serology will be summarized overall and by treatment regimen.

The proportion of presence of parasite or positive serology in babies born of mothers who were randomized and received at least one dose of either the 60- or 30-day nifurtimox treatment regimen will be calculated overall and by treatment regimen.

The results from qPCR and IHA will be summarized overall and by treatment regimen.

Signs/Symptoms of Chagas' disease will be summarized for each item (see Appendix 9.1).

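### Protocol 6.2 commits to a separate analysis of re-treated children in Part 2, but the descriptive OD, qPCR, IHA and numeric non-conventional summaries have no cut-off at rescue treatment

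*SAP*

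**What the plan says.** **Protocol.** The justification of the Part 2 selection criteria (protocol 6.2) states: "subjects who required antitrypanosomal treatment, including any investigational treatment for Chagas' disease after nifurtimox regimens will be analyzed separately". The reason it gives names both seronegative conversion and OD reduction. Protocol 6.1 asks only that a child was randomized and took at least one dose. No current Part 2 exclusion bars a child who was re-treated, and the Amendment 9 rationale (15.9.1) shows that this is intended. Protocol 5.2 and 9.2.4.4 keep re-treated children in follow-up. Protocol 9.2.4.2 has all the serology tests and qPCR sampled at every annual visit, so post-rescue values will exist.

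**SAP v3.0**, which names protocol version 11.0 as its basis:
- Part 2 analysis set (5.1): "The efficacy analyses will be done using the full analysis set (FAS), as defined in part 1", as randomized.
- General principles (4.1): "All variables collected in this study will be summarized with descriptive statistics at each assessment time". The grouping is by age stratum and regimen, and overall.
- Primary variable (6.2.2.1), the only re-treatment rule: "Subjects used antitrypanosomal drugs during the study before they were seroconverted will not be considered as sero-convertion". Their time up to the rescue drug still counts as person-time.
- OD (6.2.2.2): "Changes from baseline will be summarized to show any serial reduction of OD values".
- Exploratory outputs (6.2.2.3): "The results from qPCR and IHA will be summarized overall and by treatment regimen" and "The numeric results of non-conventional serology will be summarized overall and by treatment regimen".

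**The concern.** The example of rescue in protocol 5.2 is a child with rising ELISA OD, positive qPCR and signs or symptoms of Chagas' disease. These children are apparent failures of nifurtimox, or have been reinfected. If the rescue drug works, their later OD falls and their qPCR turns negative. A by-regimen summary without a cut-off then shows those values as though they followed the nifurtimox regimen.

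Serial OD reduction is a stated secondary objective of Part 2, so its table will be read as evidence of durable response. Protocol 6.2 foresaw the problem and said what to do. The statistical sections do not follow it up for these outputs.

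**Working it through.** **Step 1: which outputs have a rule for re-treated children?**
- Incidence rate in the 60-day arm (primary): yes, SAP 6.2.2.1. A child re-treated before conversion is not an event, and person-time stops at rescue.
- Incidence rates in the 30-day arm, by age category and by non-conventional serology: yes, because SAP 6.2.2.2 and 6.2.2.3 apply the same method to them.
- Responder proportion (conversion without cardiomyopathy) and non-conventional proportion: unclear. The 6.2.2.1 rule can be read as defining conversion throughout.
- OD change from baseline, qPCR, IHA and numeric non-conventional values: none. The rule concerns events and person-time and does not reach measured values.
- Separate set, subgroup, table or listing of re-treated children: none in the SAP, and none in protocol 10.3.2.2.

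The OD sentence does not itself mention regimen. That grouping comes from SAP 4.1 and the as-randomized full analysis set. The qPCR, IHA and numeric non-conventional sentences name it.

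**Step 2: inputs for size.** The plan gives no figure on this point to reproduce.
- N = 170 children in the 60-day arm at 48 months (SAP 6.5). For the 30-day arm I assume the same 15% drop-out: 100 × 0.85 = 85.
- k = number re-treated. The documents do not give it; k = 10 of 170 is an illustration, and five of 85 is the same fraction.
- OD falls under benznidazole (protocol 5.1): 21%, 23%, 29% and 27% at 12, 18, 24 and 48 months. I use these as stand-ins for the fall r after rescue and the mean fall m in the other children.

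**Step 3: OD, pooled against post-rescue values removed.** The difference is (k/N)(r − m).
- m = 27, r = 29: pooled (160 × 27 + 10 × 29)/170 = 27.1%; removed 27.0%. Difference 0.1 percentage points.
- m = 20 (assumed), r = 21 to 29: (10/170)(1) = 0.06 to (10/170)(9) = 0.53 points.
- m = 27, r = 21: (10/170)(−6) = −0.35 points.

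Against removal, therefore, pooling flatters nifurtimox only when the post-rescue fall exceeds the mean of the others. Against the failure itself the direction is fixed. Counting the ten with no fall gives (160 × 27 + 10 × 0)/170 = 25.4%, below both 27.1% and 27.0%.

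**Step 4: qPCR, pooled against removed.** Let p be the negative proportion in the others, and suppose all ten are negative after rescue. The difference is (160p + 10)/170 − p = (10/170)(1 − p), which is never negative. With p = 0.90 (assumed) it is 90.6% against 90.0%, or 0.6 points.

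**Step 5: does removal show the failures?** No. Removal gives 27.0%, against 25.4% with the failures counted at no fall. The number re-treated has to stand beside the summary for a reader to see this.

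**The case against.** **The protocol's own section 10 is silent.** Protocol 10.2 specifies the full analysis set as randomized, and 10.3.2.2 summarizes OD change with no rescue cut-off. The SAP reproduces both. This stands. A reader might infer a plain SAP departure from the protocol's statistical plan, but the mismatch is between protocol 6.2 and both statistical sections. It still needs resolving, because the SAP records no decision to set 6.2 aside.

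**Protocol 6.2 does not say how to separate.** This also stands. It could mean an added table or exclusion from the main one; the fix below satisfies either reading. Summarizing all observed values as randomized is a legitimate descriptive choice, but it is not the one that 6.2 announces.

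**Rescue use will be visible anyway.** In part. SAP 6.1.3 tabulates concomitant medications by regimen and drug category. That does not show how many post-rescue values enter a given OD or qPCR summary.

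**Stronger readings that the documents do not support.**
- A reader might take 27.1 − 25.4 = 1.7 OD points, or 10/170 = 5.9 qPCR points, as the gain from fixing this. Those figures compare pooling with holding re-treated children at their failed state, which neither protocol 6.2 nor the fix calls for. For qPCR, 5.9 points would also need p = 0.
- A reader might infer that the Part 2 superiority test is contaminated. The rule in SAP 6.2.2.1 prevents that.
- A reader might infer that "The proportion of subjects who show both seronegative conversion as confirmed by two assays (recombinant ELISA and IHA) and no evidence of established cardiomyopathy" is materially inflated. Even if 6.2.2.1 does not govern it, the 5% 48-month benznidazole rate in SAP 6.5 gives at most 0.05/170 = 0.03 points per re-treated child in the 60-day arm.

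**Conclusion.** The concern holds for the descriptive Part 2 summaries of OD change, qPCR, IHA and numeric non-conventional serology. Protocol 6.2 promises a separate analysis, and neither protocol 10.3.2.2 nor the SAP delivers it beyond conversion and person-time. Pooling post-rescue values by regimen tends to favour nifurtimox.

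The effect on the main summaries is probably small: about 0.1 OD points in the illustration, and (10/170)(1 − p) for qPCR. It is zero if no child is re-treated. This rests on an assumed number re-treated, on benznidazole OD falls as stand-ins, and on every re-treated child turning qPCR-negative. The documents give nothing with which to size IHA or the numeric non-conventional values.

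The outputs are secondary or exploratory and carry no success criterion. The point is worth correcting because it is cheap and implements a stated rule; it does not threaten the trial's conclusions.

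**What to change.** In SAP 6.2.2.2 and 6.2.2.3:
1. Exclude OD, qPCR, IHA and numeric non-conventional values obtained after the first non-study antitrypanosomal dose from the main by-regimen summaries.
2. Show re-treated children, with their values before and after rescue, in a separate table, as protocol 6.2 states.
3. Print the number re-treated beside each main summary, because removal alone does not show the failures.

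Optional clarification: state that a child not yet converted at that first dose is a non-responder in the responder and non-conventional proportions, with the denominator kept. This goes beyond protocol 6.2, and its effect is negligible.

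The cost is SAP wording, one flag and one table. Protocol 8.1 already has the drug name and the start and stop dates of antitrypanosomal treatment entered in the eCRF as concomitant medication. No new data are needed, and nothing changes in when rescue is given.

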## 6.2.2.3 Exploratory efficacy analysis and analysis

Exploratory efficacy variables include:

- Incidence rate of seroconversion measured and confirmed by two types of assay (recombinant ELISA and IHA) in subjects by age categories (≤2 years, >2 years to ≤6 years, >6 to ≤12 years, >12 to <18 years; age is defined as subject's age at randomization)
- Proportion of presence of parasite or positive serology in babies born of mothers who were randomized and received at least one dose of either the 60- or 30-day nifurtimox treatment regimen
- Proportion of responders and incidence rate of seronegative conversion as confirmed by non-conventional serology in subjects who were randomized and received at least one dose of either 60- or 30-day nifurtimox treatment regimens

Analysis of exploratory efficacy variables

The same method for calculating incidence rate and its 2-sided 95% CI of the primary efficacy variable will be applied on the following variable:

Statistical Analysis Plan

- Incidence rate of nifurtimox subjects with seronegative conversion in all subjects by age categories. The age categories are grouped as  $\leq 2$  years,  $\geq 2$  years to  $\leq 6$  years,  $\geq 6$  to  $\leq 12$  years,  $\geq 12$  to <18; age is defined as subject's age at randomization
- Incidence rate of seronegative conversion as confirmed by non-conventional serology in subjects who were randomized and received at least one dose of either 60- or 30- day nifurtimox treatment regimens

The proportion of subjects with seronegative conversion as confirmed by non-conventional serology will be calculated overall and by treatment regimen. The numeric results of non-conventional serology will be summarized overall and by treatment regimen.

The proportion of presence of parasite or positive serology in babies born of mothers who were randomized and received at least one dose of either the 60- or 30-day nifurtimox treatment regimen will be calculated overall and by treatment regimen.

The results from qPCR and IHA will be summarized overall and by treatment regimen.

Signs/Symptoms of Chagas' disease will be summarized for each item (see Appendix 9.1).

6.3 Safety

**Bayer HealthCare** 

Part 1 (CHICO)

## Safety Variables

Safety variables include adverse events (AEs), physical examination abnormalities, vital signs, ECG, hematology and blood chemistry, coagulation, and urinalysis. All analyses of safety variables will be descriptive only, no formal testing will be performed.

## **Adverse Events**

All adverse events occurring during the study (i.e., from signing of informed consent until last visit) will be reported. The MedDRA coding system will be used to code the adverse events.

An overview of frequencies of subjects who died, experienced any adverse event, experienced any drug-related adverse event, experienced a serious adverse event (SAE), experienced a drug-related serious adverse event, or discontinued due to an adverse event will be summarized by treatment regimen.

Adverse events will be considered treatment emergent, if they first occurred or worsened at or after first application of study medication during the course of the study up to and including 7 days after last application of study medication.

Incidence of treatment emergent AEs (TEAEs), drug-related TEAEs, serious TEAEs, drugrelated serious TEAEs, as well as TEAEs leading to discontinuation will be summarized by primary system organ class and high level term by treatment regimen.

The definitions of incidence are as follows:

- Incidence of all events: # of subjects reporting the event with a start date during or after treatment/# of subjects valid for safety.
- Incidence of drug-related events: # of subjects reporting a drug-related event with a start date during or after treatment/# of subjects valid for safety.
- Incidence of events by maximum intensity: # of subjects reporting the event at the indicated intensity with a start date during or after treatment/# of subjects valid for safety.

Adverse events leading to death, premature discontinuation and serious adverse events will be listed. In this study, all AEs of urticarial, weight loss of > 20%, severe rash, and severe polyneuropathy will be considered AEs of special safety interest. Adverse events of special safety interest will be summarized by treatment regimen.

AEs occurring between the time of consent and the first dose of study drug will be summarized separately.

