5.1 Part 1 (CHICO)

Design overview

This is a Phase 3, prospective, randomized (to dosing regimen), age-stratified, double-blind, parallel-group study to evaluate the efficacy, safety/tolerability, and PK of oral administration of nifurtimox in children with a diagnosis of Chagas' disease.

A schematic of part 1 (CHICO) of the study design is presented in Figure 5–1.

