Also, for reasons of patient safety and at the discretion of the investigator, a subject may be asked to take a "drug holiday" [interruption of study drug administration] or a reduced daily dosage may be requested by the investigator from the depot. A decision by the investigator for drug holiday or reduced dosage will be based on the occurrence and/or severity of adverse effects, and/or the clinical status of the subject. Any and all changes to study drug administration or daily dosage must be recorded within the subject's study chart, as well as, the electronic case report form (eCRF).⁶⁹

Primary variable(s)

The primary efficacy variable will be sero-reduction or sero-conversion at 12 months post-treatment using two conventional ELISA serology tests as the measure of efficacy.⁷⁰

Justification of the design

This study uses an historical untreated-controlled design, as it is unethical to have a prospective placebo-controlled superiority study design. Only two benznidazole placebo-controlled studies have been conducted in children with Chagas' disease.[15][16] Direct comparisons between these studies cannot be made due to differences in study populations (Argentina vs. Brazil), medication dosage (5 mg/kg vs. 7.5 mg/kg), outcome measures, and time of follow-up (4 years vs. 3 years). Data derived from these studies will, however, be used as the comparative historical placebo control to be utilized in the analysis of the study endpoints. Hence, a comparison of sero-reduction and/or sero-conversion from baseline to 12-month follow-up for both primary and secondary endpoint evaluations (versus

⁶⁵ Text deleted/added for clarity (Amendment 1)

⁶⁶ Modified as per amendment 4

⁶⁷ Text modified/deleted for clarity, and per Modifications 9 and 10 (Amendment 1)

⁶⁸ Text added per Modification 11 (Amendment 1)

⁶⁹ Text modified as per amendment 4

⁷⁰ Text modified per Modification 2 (Amendment 1)

	Integrated Clinical Study Protocol	
	BAY A2502 / 16027	
03 NOV 2020	Version 11.0	Page: 31 of 259

historical placebo) will be made as well as for a comparison with benznidazole. Details are presented in Section $10.^{71}$

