Safety variables will be summarized by means of descriptive statistics and/or frequency tables as appropriate. Summaries will be given by treatment regimen. All post-treatment AEs and SAEs, as well as drug-related AEs and SAEs, will be summarized by MedDRA terms.¹⁹⁰ AEs occurring between the time of consent and the first dose of study drug will be summarized separately. Subjects experiencing urine discoloration from riboflavin ingestion will be listed also, although these incidences will not necessarily be considered AEs.

¹⁸⁴ Text deleted per Modification 2 (Amendment 1)

¹⁸⁵ Text modified as of amendment 2

¹⁸⁶ "Exploratory" added per Amendment 5.

¹⁸⁷ Text modified/added for clarity (Amendment 1)

¹⁸⁸ Sentence added per Amendment 5.

¹⁸⁹ Replaced IFA with IHA per Amendment 6.

¹⁹⁰ Text modified as of amendment 2

03 NOV 2020 Version 11.0

Missing data/drop outs

No imputations will be made for missing data due to dropouts or other causes. For the primary efficacy analysis done on the FAS, a patient without an assessment at the primary 12 month time point will be considered a treatment failure. For the secondary analysis using the PPS, patients who do not have serology determinations to assess the primary endpoint will be excluded from the analysis.

The following sensitivity analyses for the primary efficacy variable will be performed:

• Missing values due to the following reasons treated as treatment failures and other missing values excluded from analysis:¹⁹¹

1. the reason for discontinuation is known or suspected to be treatment ineffectiveness or an AE

2. a subject has not had a negative serology at any visit and has no serology determination for the primary analysis visit

3. an indeterminate or incorrectly performed serology determination occurs at the primary analysis visit.¹⁹²

- Observed data only
- Analysis on PPS

Pharmacokinetic data

Specifications for PK data analysis will be provided in a separate document. Plasma concentration vs time data documented within the study report will be analyzed descriptively using univariate statistics.¹⁹³

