After study eligibility has been confirmed and safety assessments have been performed at Visit 2 (Day 1), subjects will be randomized via Interactive Voice Response System/Interactive Web Response System (IVRS/IWRS) in a 2:1 ratio (60-day regimen vs. 30-day regimen) to one of two treatment groups:

- Nifurtimox tablets administered three times daily for 60 days (Days 1 60, active nifurtimox treatment, Treatment Group 1) or
- Nifurtimox tablets administered three times daily for 30 days, followed by nifurtimox placebo administered three times daily for 30 days (Days 1 30, active nifurtimox treatment; Days 31 60, placebo; Treatment Group 2).

The study is composed of 3 periods:

- Screening period
- Treatment period
- Follow-up period

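### Adverse-event incidence is tabulated only cumulatively by regimen, so the planned tables do not isolate the one concurrent nifurtimox-versus-placebo contrast (Days 31-60)

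*SAP*

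**What the plan says.** **Treatment.** The design overview in SAP 3.1 gives one arm "Nifurtimox tablets administered three times daily for 60 days" and the other "Nifurtimox tablets administered three times daily for 30 days, followed by nifurtimox placebo administered three times daily for 30 days". Protocol 5.1 describes the trial as "randomized (to dosing regimen), age-stratified, double-blind". The efficacy control is historical because, in the words of the protocol's design justification, "it is unethical to have a prospective placebo-controlled superiority study design".

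**Adverse-event tables.** SAP 6.3 (Adverse Events) counts an event as treatment-emergent from first dose "up to and including 7 days after last application of study medication". Protocol 9.6.1.3 makes clear that Part 1 study medication includes placebo, so in the 30-day arm this window runs through the placebo month. The tables are laid out "as well as TEAEs leading to discontinuation will be summarized by primary system organ class and high level term by treatment regimen". The incidence definitions that follow divide children with any event starting during or after treatment by all children valid for safety. Protocol 10.3.2.1 (Safety) says "Summaries will be given by treatment regimen". The only time split planned for adverse events is the separate summary of events between consent and first dose.

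**Other safety data.** SAP 6.3 summarises laboratory values, ECG data and vital signs by visit and regimen. The incidence of high and low laboratory abnormalities is pooled over all time after the start of treatment. All safety analyses are descriptive.

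**The concern.** Evaluating the tolerability of nifurtimox in children is a secondary objective of Part 1, and the trial has no separate untreated arm. The second month nevertheless contains a randomised comparison of nifurtimox with matching placebo. Neither document plans an adverse-event table by onset before or after the switch, or a denominator of children who began the second month's supply.

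In a cumulative table each child counts once. A child with a given event in the first month, when treatment is the same in both arms, is already counted and cannot add to the contrast that the second month creates. Near-equal columns could therefore be read as evidence that the second month of drug adds little, when shared first-month events alone can produce that pattern.

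**Working it through.** **1. The plan's own precision figure.** Neither document states a precision figure for adverse events. The nearest one is in protocol 10.4: a half-width of about 0.12 for the 95% CI of a difference between 200 and 100 children. At p = 0.5:

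1.96 × sqrt(0.25/200 + 0.25/100) = 1.96 × 0.0612 = 0.120.

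The figure reproduces.

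**2. Formula.** Let f be the risk of a given event on Days 1-30 (same drug in both arms), and let q (nifurtimox) and r (placebo) be the risks on Days 31-60. Assume that the months are independent. Then:

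- 60-day arm, cumulative: 1 - (1-f)(1-q)
- 30-day arm, cumulative: 1 - (1-f)(1-r)
- difference: (1-f)(q-r)

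The planned table thus multiplies the second-month difference by (1-f): 0.95 at f = 5%, 0.70 at 30% and 0.50 at 50%.

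**3. Worked example** (assumed rates; 200 versus 100 children). Take f = 30%, q = 20%, r = 10%.

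- Cumulative: 1 - 0.7 × 0.8 = 44% versus 1 - 0.7 × 0.9 = 37%. The difference is 7 points, SE = sqrt(0.44 × 0.56/200 + 0.37 × 0.63/100) = 0.0597, z = 1.17.
- Days 31-60: 20% versus 10%. The difference is 10 points, SE = sqrt(0.20 × 0.80/200 + 0.10 × 0.90/100) = 0.0412, z = 2.43.
- With f = 50%, cumulative: 60% versus 55%, z = 0.83.
- With 10% of children gone by Day 31 (180 versus 90), Days 31-60: z = 2.30.

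The z-values only index signal against noise; no safety test is planned.

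**4. Range.** The documents give no paediatric adverse-event rates. The benefit-risk section of the protocol gives 50% to 75% for gastrointestinal effects in adults and says that reactions in children are milder and less frequent. The rates below are therefore assumptions, with r = q/2, so the true second-month risk ratio is 2.0 throughout.

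| f | q vs r, Days 31-60 | Difference (points) | Cumulative | Difference (points) | Risk ratio |
|---|---|---|---|---|---|
| 5% | 5% vs 2.5% | 2.5 | 9.8% vs 7.4% | 2.4 | 1.32 |
| 10% | 10% vs 5% | 5.0 | 19% vs 14.5% | 4.5 | 1.31 |
| 30% | 30% vs 15% | 15.0 | 51% vs 40.5% | 10.5 | 1.26 |
| 50% | 50% vs 25% | 25.0 | 75% vs 62.5% | 12.5 | 1.20 |
| 60% | 20% vs 10% | 10.0 | 68% vs 64% | 4.0 | 1.06 |

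In the fourth row from the bottom of the range upwards (f = 10% to 50%) both measures shrink visibly. At 5% the absolute difference is almost intact, and the loss is in the risk ratio.

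**5. What if first-month events persist?** Step 3 counts every child as able to have the event in the second month. A table of new onset or worsening does not. In the limiting case where every first-month event continues unchanged, the Day 31-60 table shows 0.7 × 20% = 14% versus 0.7 × 10% = 7%. That is the same 7 points as the cumulative table. SE = sqrt(0.14 × 0.86/200 + 0.07 × 0.93/100) = 0.0354, so z is about 2.0. The precision gain largely survives; the gain in absolute difference does not.

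**The case against.** **The regimen tables answer the trial's own question.** The randomised contrast is 60 days against 30 days, and cumulative incidence by regimen describes it correctly. This stands. A reader might infer that the 30-day column describes neither drug nor placebo, or that the tables make the regimens look more alike than they are. Neither follows: the column describes the 30-day regimen, and 44% versus 37% would be the true difference between regimens. What is missing is a different quantity, drug against placebo in the second month.

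**Much of the contrast is visible elsewhere.** A reader might infer that no safety data separate the two months. Laboratory, ECG and vital-sign values are tabulated by visit, so Day 30 and Day 60 can be compared by arm. Serious events and events leading to discontinuation are listed. The gap is limited to incidence tables.

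**A general rule may cover it.** SAP 4.1 promises descriptive statistics for all variables at each assessment time. This does not settle the matter, because SAP 6.3 specifies cumulative incidence for adverse events.

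**The second-month contrast has weaknesses.** These also stand. The placebo contains riboflavin, and protocol 7.4 calls bright yellow urine a common effect, so blinding is weakest in that month. The SAP's own 7-day rule implies that early placebo events may carry over from drug. Protocol 5.1 allows interruptions and dose reductions, which blur exposure. Restricting to children who start the second kit conditions on an event after randomisation, although selection up to that point occurs under identical treatment. These limits should be stated with the table; they do not justify leaving it out.

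**It can be done later.** True, since the dates exist, but a table specified in advance is more credible than one requested after the results are seen.

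**Conclusion.** The planned tables are valid for comparing regimens but do not isolate the only concurrent nifurtimox-versus-placebo contrast for adverse events. The gap covers adverse-event incidence and the pooled high/low laboratory-abnormality incidence, and nothing wider. It should be filled, because tolerability is a stated objective.

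Under independence between months, the cumulative difference is (1-f) times the second-month difference. That is a large loss for common or front-loaded events and almost none in absolute terms for rare ones, where mainly the risk ratio suffers. The example's z-values of 1.17 and 2.43 rest on assumed rates and on first-month events having resolved.

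A reader might take the pooling period to be exactly 60 days. It is longer: TEAEs run to 7 days after last dose, and the incidence definitions set no end.

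**What to change.** Keep the regimen tables. Add to SAP 6.3 descriptive tables of TEAEs, drug-related TEAEs, serious TEAEs, adverse events of special interest and TEAEs leading to discontinuation, by onset period:

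- **(a)** First dose to the day before the first dose of the Visit 6 kit, pooled over arms and by arm.
- **(b)** First dose of the Visit 6 kit to last dose plus 7 days, by arm, among children who started that kit. Count new onset or worsening, and give the risk difference with a 95% CI.
- Events ongoing at the switch, by arm, because (b) does not count them again.
- A version of (b) that omits the first 7 days in both arms, to allow for carry-over.

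State the limits beside the tables: possible unblinding through riboflavin, drug interruptions and dose reductions, and conditioning on reaching the second kit. Splitting at the kit date rather than at Day 30 deals with the ±3-day window for Visit 6.

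The cost is SAP wording and one extra set of tables. Event start dates are already needed for the TEAE definition, and SAP 6.1.4 already uses start and stop dates for each drug distribution. Confidence intervals are compatible with a descriptive safety analysis. No new data or visits are needed.
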